7.3.3 Modified Cigarette Evaluation Questionnaire

The MCEQ (Cappelleri et al. 2007) will be completed by the subject him/herself daily from Day -1 to Day 5 between 08:00 PM and 11:00 PM, for the CC and THS 2.2 arms only to assess the degree to which subjects experience the reinforcing effects of smoking.

The MCEQ consists of 12 items as presented in Table 5.

Table 5: Modified Cigarette Evaluation Questionnaire - Questions and Subscales

	Question	Subscale
1	Was smoking satisfying?	Smoking Satisfaction
2	Did cigarettes taste good?	Smoking Satisfaction
3	Did you enjoy the sensation in your throat and chest?	Enjoyment of Respiratory Tract Sensations
4	Did smoking calm you down?	Psychological Reward
5	Did smoking make you feel more aware?	Psychological Reward
6	Did smoking make you feel less irritable?	Psychological Reward
7	Did smoking help you concentrate?	Psychological Reward
8	Did smoking reduce your hunger for food?	Psychological Reward
9	Did smoking make you dizzy?	Aversion
10	Did smoking make you nauseous?	Aversion
11	Did smoking immediately relieve your craving for a cigarette?	Craving Reduction
12	Did you enjoy smoking?	Smoking Satisfaction

Items are assessed on a 7-point scale, ranging from 1 (not at all) to 7 (extremely). Higher scores indicate greater intensity on that scale.

The subscales scores will be derived by averaging the individual non-missing item scores if at least 50% are non-missing, otherwise the subscale score will be set to missing.

7.3.4 Minnesota Nicotine Withdrawal Scale (revised edition) Questionnaire

The MNWS (Hughes and Hatsukami 2008) is a 24 hour recall that will be completed by the subject him/herself daily on Day 0 to Day 6 prior to product use to reflect the previous days experience. Therefore although it is collected on Days 0 to 6 it will be reported as Days -1 to 5. Only the self-reported part of the MNWS will be used.

The self-reported part of the MNWS consists of the following 15 items which are rated over the last 24 hours on a scale of 0 to 4 (see Table 6). Higher scores indicate greater intensity on that scale.

The total scores will be derived by summing the individual item scores if all items are non-missing, otherwise the total score will be set to missing. The first total score calculated by summing the first 9 items is based on validated items, the second score is

based on 6 extra items which are thought to have an impact on withdrawal but have not been validated.

Table 6: Minnesota Nicotine Withdrawal Scale (Revised Edition) Questionnaire Scores

	Question	Total Score
1	Angry, irritable, frustrated.	1 and 2
2	Anxious, nervous.	1 and 2
3	Depressed mood, sad.	1 and 2
4	Desire or craving to smoke.	1 and 2
5	Difficulty concentrating.	1 and 2
6	Increased appetite, hungry, weight gain.	1 and 2
7	Insomnia, sleep problems, awakening at night.	1 and 2
8	Restless.	1 and 2
9	Impatient.	1 and 2
10	Constipation	2
11	Dizziness	2
12	Coughing	2
13	Dreaming or nightmares	2
14	Nausea	2
15	Sore throat	2

If the baseline score is 0, the percent change from baseline will be calculated using a value of 1 for the denominator.

7.3.5 Human Smoking Topography Questionnaire

The HST questionnaire will be completed on Days 0 and 4 by all subjects smoking CC that are compatible with the HST SODIM® device (i.e., non-slim CC) to evaluate the impact of the use of the HST SODIM® device.

The HST questionnaire has 5 items rated on a 5-point Likert scale (strongly agree, agree, neither agree nor disagree, disagree and strongly disagree). The items are:

1. The smoking of the conventional cigarettes/products is different with the device.
2. You enjoy smoking with the device as much as without it.
3. The taste of the conventional cigarettes/products is different with the device.
4. The device is easy to use.
5. Your smoking is disturbed by the device.

7.3.6 Cough Assessment

Subjects will be asked to assess the respiratory symptom 'cough' using a VAS, three Likert scale questions, and one open ended question on a daily basis during the confinement period (on Day 0 to Day 6) prior to start of product use/smoking and no later than 10:00 PM. Although the symptoms are assessed on Days 0 to 6 the data reflects the

subjects respiratory symptoms from the previous day (Days -1 to Day 5) and therefore will be reported as Days -1 to Day 5 .

Subjects will be asked if they have experienced a regular need to cough, e.g., whether they have coughed several times in the previous 24 hours prior to assessment. If the answer is 'yes', subjects will be asked to complete questionnaire.

The VAS will assess how bothersome cough is to the subject ranging from 'not bothering me at all' to 'extremely bothersome', and this will be given a numeric value between 0 and 100, measured on a 100 mm scale.

Subjects will also be asked to assess the intensity and frequency of cough and the amount of sputum production on Likert scales as presented in **Table 7 “ Cough Assessment Likert Scales”**.

Table 7 Cough Assessment Likert Scales

Question	Likert Scale
1 The intensity of cough	1 = very mild 2 = mild 3 = moderate 4 = severe 5 = very severe
2 The frequency of cough	1 = rarely 2 = sometimes 3 = fairly often 4 = often 5 = almost always
3 The amount of sputum production	0 = no sputum 1 = a moderate amount of sputum; 2 = a larger amount of sputum; 3 = a very large amount of sputum.

7.4 Human Smoking Topography Assessment

The HST SODIM® device measures and records the flow and other per-puff parameters listed below (**Table 8**). From the per-puff parameters, the per-cigarette parameters shown below will be derived (representing average values or totals per cigarette (**Table 9**). Prior to calculation of the per-cigarette parameters, the topography data will be processed through analysis software. Only data that are able to be processed by the software will contribute to the per-cigarette parameters and will be part of the study database.

**Table 8: HST- Per-Puff Parameters**

Description	Variable	Unit
Puff number	Ni	
Puff volume	Vi	mL
Puff duration	Di	s
Average flow [Vi/Di]	Qmi	mL/s
Peak flow	Qci	mL/s
Inter puff interval	Ii	s
Sum of Ii and Di	DFi	s
Work [INT Pmi*FinalFlow*dt]	Wi	mJ
Average pressure drop	Pmi	mmWG
Peak pressure drop	Pci	mmWG
Average resistance [Pmi/Qmi]	Rmi	mmWG/mL/s
Peak resistance [Pci/Qci]	Rci	mmWG/mL/s

Table 9: HST - Per-Cigarette Parameters

Description	Variable	Formula	Unit
Total number of puffs	NPC	$\sum Ni$	
Total puff volume	TVOL	$\sum Vi$	mL
Average puff volume	AvgVi	$\sum Vi / NPC, i=1 \dots NPC$	mL
Average puff duration	AvgDi	$\sum Di / NPC, i=1 \dots NPC$	s
Total puff duration	TDi	$\sum Di$	s
Average flow	AvgQmi	$\sum Qmi / NPC, i=1 \dots NPC$	mL/s
Average Peak flow	AvgQci	$\sum Qci / NPC, i=1 \dots NPC$	mL/s
Total inter puff interval	Tli	$\sum Ii$	s
Average inter puff interval	Avgli	$\sum Qci / NPC, i=1 \dots NPC$	s
Total smoking duration	TDFi	$\sum DFi$	s
Total Work	TWi	$\sum Wi$	mJ
Average Work	AvgWi	$\sum Wi / NPC, i=1 \dots NPC$	mJ
Average pressure drop	AvgPmi	$\sum Pmi / NPC, i=1 \dots NPC$	mmWg
Average Peak pressure drop	AvgPci	$\sum Pci / NPC, i=1 \dots NPC$	mmWg
Smoking Intensity	SMINT	$TVOL/TDFi$	mL/s
Puffing Time Index	PTI	$(100 * TDi) / TDFi$	%
Puff Frequency	PFeq	$NPC / (TDFi / 60)$	puffs/min

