| Description | Variable | Unit |
|------------------------------|----------|-----------|
| Puff number | Ni | |
| Puff volume | Vi | ml |
| Puff duration | Di | s |
| Average flow [Vi/Di] | Qmi | ml/s |
| Peak flow | Qci | ml/s |
| Inter puff interval | Ii | s |
| Sum of Ii and Di | DFi | s |
| Work [INT Pmi*FinalFlow*dt] | Wi | mJ |
| Average pressure drop | Pmi | mmWG |
| Peak pressure drop | Pci | mmWG |
| Average resistance [Pmi/Qmi] | Rmi | mmWG/ml/s |
| Peak resistance [Pci/Qci] | Rci | mmWG/ml/s |

Table 5. Human Smoking Topography - Per-Cigarette Parameters

| Description | Variable | Formula | Unit |
|-----------------------|----------|---------------------------------|------|
| Total number of puffs | NPC | $\sum Ni$ | |
| Total puff volume | TVOL | $\sum Vi$ | ml |
| Average puff volume | AvgVi | $\sum Vi / NPC, i=1 \dots NPC$ | ml |
| Average puff duration | AvgDi | $\sum Di / NPC, i=1 \dots NPC$ | s |
| Total puff duration | TDi | $\sum Di$ | s |
| Average flow | AvgQmi | $\sum Qmi / NPC, i=1 \dots NPC$ | ml/s |
| Peak flow | AvgQci | $\sum Qci / NPC, i=1 \dots NPC$ | ml/s |

Confidentiality statement: Data and information contained in this document are considered to constitute trade secrets and confidential commercial information, and the legal protections provided to such trade secrets and confidential information are hereby claimed under the applicable provisions of applicable law. No part of this document may be publicly disclosed without the written consent of Philip Morris Products S.A.

| Description | Variable | Formula | Unit |
|-----------------------------|------------------|------------------------------------|------|
| Total inter puff interval | Tli | $\sum I_i$ | s |
| Average inter puff interval | AvgIi | $\sum Q_{ci} / NPC, i=1 \dots NPC$ | s |
| Total smoking duration | TDFi | $\sum DF_i$ | s |
| Total Work | TWi | $\sum W_i$ | mJ |
| Average Work | AvgWi | $\sum W_i / NPC, i=1 \dots NPC$ | mJ |
| Average pressure drop | AvgPmi | $\sum P_{mi} / NPC, i=1 \dots NPC$ | mmWg |
| Average Peak pressure drop | AvgPci | $\sum P_{ci} / NPC, i=1 \dots NPC$ | mmWg |
| Smoking Intensity | SMINT | TVOL/TDFi | ml/s |
| Puffing Time Index | PTI | $(100*TD_i)/TDF_i$ | % |
| Puff Frequency | PF _{eq} | $NPC/(TDF_i/60)$ | |

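### The plan defines average inter-puff interval with the symbol for peak flow, so the endpoint as written duplicates average peak flow under a label in seconds.

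*SAP*

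**What the plan says.** SAP Section 7.4 derives the per-cigarette topography parameters in Table 9 from the per-puff parameters in Table 8. The relevant rows are:

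- Table 8, peak flow: "Peak flow Qci mL/s".
- Table 8, interval: "Inter puff interval Ii s".
- Table 9, average peak flow: "Average Peak flow AvgQci $\sum Qci / NPC, i=1 \dots NPC$ mL/s".
- Table 9, total interval: "Total inter puff interval Tli $\sum Ii$ s".
- Table 9, average interval: "Average inter puff interval Avgli $\sum Qci / NPC, i=1 \dots NPC$ s".

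Protocol Table 5 (Section 7.8.1.1) has the same content for the last row: "Average inter puff interval | AvgIi | $\sum Q_{ci} / NPC, i=1 \dots NPC$ | s".

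SAP Section 5.3 names average inter-puff interval as an exploratory endpoint. SAP Section 12.6.3.2 has the per-cigarette parameters summarised, plotted and compared between THS 2.2 and CC. The comparison is an ANCOVA on the log scale, run separately for Days 1 and 4, and reports a ratio with a 95% CI. SAP Section 9, which lists departures from the protocol's analysis, does not mention this formula.

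**The concern.** One expression cannot be both a flow in mL/s and a time in seconds. The label, the variable name and the unit of the row all say interval, while the formula says peak flow. The row between the two averages uses Ii correctly for the total, which shows the symbol that was meant.

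The formula stands in two separately prepared documents, so it is not a fault of PDF reading. The SAP table was also revised after the protocol: the peak-flow row gained the word average, and puff frequency gained a unit. The wrong symbol survived that revision.

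Table 9 is the derivation rule for a named endpoint. Someone programming or checking to the approved SAP would validate the wrong variable, and code that correctly uses Ii would disagree with the SAP.

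**Working it through.** No sample size, power or alpha figure is involved. The check compares symbols and units, with one numerical illustration.

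**1. The rule as printed.** From SAP Table 9:

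- average peak flow: AvgQci = ΣQci / NPC
- average interval as printed: AvgIi = ΣQci / NPC

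The right-hand sides are identical, so AvgIi = AvgQci for every cigarette, whatever the values of Ii.

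**2. Units.** Qci is in mL/s and NPC is a count, so ΣQci / NPC is in mL/s. The table gives s.

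**3. What the tables' own symbols imply.** The total interval is TIi = ΣIi, so the mean on the printed divisor is ΣIi / NPC = TIi / NPC, in seconds. Table 8 defines DFi as Ii + Di, so ΣIi can also be obtained as TDFi − TDi, that is, total smoking duration minus total puff duration. The two routes must agree.

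**4. Illustration on assumed data** (the documents give no puff-level values). Take one cigarette of ten puffs:

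- Peak flows 45, 44, 42, 40, 40, 38, 38, 36, 35 and 34 mL/s; the sum is 392 and 392 / 10 = 39.2 mL/s.
- Puff durations summing to 14.7 s.
- A constant interval, set in turn to 5, 10, 20 and 30 s.

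| Interval (s) | Printed formula | AvgQci | ΣIi / NPC | (TDFi − TDi) / NPC |
|---|---|---|---|---|
| 5 | 39.2 | 39.2 | 5 | 5 |
| 10 | 39.2 | 39.2 | 10 | 10 |
| 20 | 39.2 | 39.2 | 20 | 20 |
| 30 | 39.2 | 39.2 | 30 | 30 |

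For the first row, TDFi = 10 × 5 + 14.7 = 64.7 and (64.7 − 14.7) / 10 = 5. The printed formula does not respond to the interval at all. The formula with Ii returns it exactly.

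**5. Consequence for the analysis.** The equality holds cigarette by cigarette, so it holds however cigarettes are combined within a subject and day, provided both parameters are combined in the same way. The response and the baseline covariate would then be the same in both ANCOVA models, as would the estimated ratio and its CI. Only the label and unit would differ.

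**6. Reach of the error.** No other row of Table 9 uses AvgIi. Total interval, total smoking duration, smoking intensity, puffing time index and puff frequency are all built from other quantities.

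**The case against.** The strongest reply is that the slip is obvious. It looks like a copied cell, its label and unit contradict it, and a competent programmer would use Ii. SAP Section 7.4 sends the topography data through analysis software before the per-cigarette values are calculated, and protocol Section 7.8.1.1 has the sponsor's topography group validate the data first. Total interval and number of puffs are separate endpoints and the parameters are listed, so the mean interval can be rebuilt as TIi / NPC. The parameter is one of 17 exploratory topography measures and plays no part in the success criterion.

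Most of this stands, and it limits the point. A reader might infer that the reported interval will be wrong, or that information on puffing interval is lost. The documents support neither: the code is not shown, and the interval data are kept. What remains is that the approved derivation rule is wrong and nothing in either document corrects it.

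A reader might also see a second, larger error in "Total number of puffs NPC $\sum Ni". Table 8 labels Ni as puff number. If that were a running index, ten puffs would give 10 × 11 / 2 = 55, and every average would be distorted. The table excludes this reading. NPC is labelled as the total number of puffs. The averages are summed from i = 1 to NPC, so with NPC = 55 they would run over 45 puffs that do not exist. Puff frequency is NPC over minutes, in puffs/min. NPC is therefore a count, loosely written.

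Nor is there an error in the divisor. The documents do not say whether the last puff has an interval, but both tables state NPC as the denominator. Whether NPC − 1 was meant is at most a request for clarification.

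**Conclusion.** The point holds for one symbol in each document. SAP Table 9 and protocol Table 5 define average inter-puff interval through peak flow. Followed as written, this endpoint duplicates average peak flow for every cigarette, and its THS 2.2:CC ratio and CI on Days 1 and 4 carry no information on puffing interval. That follows from the tables alone and needs no assumed data; the ten-puff example only illustrates it.

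The conclusion is conditional on the program following the printed formula, which the documents do not settle either way. The effect is limited to one exploratory parameter that can be recovered from others. Primary and secondary endpoints, power and alpha are unaffected. The correction should be made, but it does not bear on the study's main conclusions.

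**What to change.** In SAP Table 9 and protocol Table 5, replace Qci with Ii in the average-interval row, so that AvgIi = ΣIi / NPC in seconds. Confirm that the derivation program uses Ii. A simple test is that AvgIi equals TIi / NPC for each cigarette and does not equal AvgQci throughout.

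As a wording note only, the formula for NPC could be rewritten as the count of puffs, which its label and the summation limits already show is intended.

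The cost is one symbol in each of two tables and one programming check. Nothing changes in data collection, sample size or study procedures.

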7.5 Categorical Variables

The categorical variables used in this study are shown below (Table 10).

**Table 10: Categorical Variables Definitions**

Variable	Categories
BMI (kg/m ²)	Underweight: < 18.5 Normal range: ≥ 18.5 and < 25.0 Overweight: ≥ 25.0 and < 30.0 Obese: ≥ 30.0
FTND total score	Mild: 0 - 3 Moderate: 4 - 6 Severe: 7 - 10
Daily CC consumption over the last 4 weeks as reported at Screening (per day).	10-19 >19
CO breath test level (ppm)	≤ 10 > 10
COHb level	≤ 2% > 2%
Adverse event severity	Mild Moderate Severe
Adverse event relationship	Related Not related
Adverse event expectedness	No Yes
Action taken with study product due to adverse event	Product use interrupted Product use stopped Product use reduced Not applicable None
Outcome of adverse event	Death related to adverse event Not recovered or not resolved Recovered or resolved Recovered or resolved with sequelae Recovering or resolving Unknown
Seriousness Criteria	Fatal Life-threatening Requires hospitalization Results in disability/incapacity Congenital anomaly/birth defect
Severity of device event	Major Minor

8 SAMPLE SIZE JUSTIFICATION

The following discussion addresses the ability to demonstrate on Day 5 a reduction of at least 50% on four selected primary BoExp in smokers switching from CC to THS 2.2 as compared to smokers continuing to smoke CC.

Table 11 describes the expected coefficients of variation (CV) and mean ratios (MR) between THS 2.2 and the two control arms in COHb, 3-HPMA, MHBMA and S-PMA on Day 5 based on data from a controlled, randomized, open-label, 3-arm parallel single-center confinement study that investigated exposure to selected smoke constituents in smokers switching from CCs to smoking article (SMAR) cigarettes for 5 days, the YVD-CS01-EU study (ClinicalTrials.gov: ID: NCT00812279) sponsored by PMI. The mean ratios and CVs for SMAR/CC are expected to be the same as THS 2.2/CC.

Table 11: Coefficients of Variation (YVD-CS01-EU study)

	THS 2.2 /CC MR (CV)	THS 2.2 /SA MR (CV)
COHb	0.40 (0.32)	2.10 (0.20)
3-HPMA	0.30 (0.50)	1.70 (0.33)
MHBMA	0.15 (0.70)	1.00 (0.35)
S-PMA	0.20 (0.70)	1.15 (0.42)

Abbreviations: 3-HPMA = 3-hydroxypropylmercapturic acid; CC = conventional cigarettes; COHb = carboxyhemoglobin; CV = coefficient of variation; MHBMA = monohydroxybutenyl mercaptyuric acid; MR = mean ratio; S-PMA = S-phenylmercapturic acid; SA = smoking abstinence; THS 2.2 = Tobacco Heating System 2.2.

Table 12 describes the expected CV and MR between THS 2.2 and the CC control arm in COHb, 3-HPMA, MHBMA, S-PMA based on data from a single-center, open-label, randomized, controlled, 2-arm parallel group study to evaluate the exposure to selected smoke constituents in smoking, apparently healthy subjects switching from CC to THS 2.1 compared to subjects continuing to smoke CC for 5 days, the ZRHX-EX-01 study (ClinicalTrials.gov: ID: NCT01780714) sponsored by PMI. The mean ratios and coefficients of variations for THS 2.1/CC are expected to be the same as THS 2.2/CC.

Table 12: Coefficients of Variation (ZRHX-EX-01 study)

	THS 2.2 /CC MR (CV)
COHb	0.44 (0.14)
3-HPMA	0.28 (0.20)
MHBMA	0.11 (0.47)
S-PMA	0.07 (0.50)

Abbreviations: 3-HPMA = 3-hydroxypropylmercapturic acid; CC = conventional cigarettes; COHb = carboxyhemoglobin; CV = coefficients of variation; MHBMA = monohydroxybutenyl mercaptyuric acid; MR = mean ratios; S-PMA = S-phenylmercapturic acid; THS 2.2 = Tobacco Heating System 2.2.

Based on these two sets of assumptions, the power to demonstrate a reduction was computed. **Table 13** describes the expected power to demonstrate a reduction on 4 primary BoExp in smokers switching from CC to THS 2.2 as compared to those continuing to smoke CC, using one-sided test with 2.5% type I error probability using the assumptions from YVD-CS01-EU and ZRHX-EX-01 and 160 smokers (80 in THS 2.2, 40 in CC, and 40 in the SA arm).

**Table 13: Expected Power (YVD-CS01-EU and ZRHX-EX-01 Studies Assumptions)**

Assumptions	Reduction					
	50%	51%	52%	53%	54%	55%
YVD-CS01-EU	96%	91%	85%	75%	63%	48%
ZRHX-EX-01	>99%	>99%	96%	81%	48%	16%

A total of 160 smokers (80 in THS 2.2, 40 in CC, and 40 in the SA arm) will be randomized to demonstrate a reduction of at least 50% on 4 primary BoExp in smokers switching from CC to THS 2.2 as compared to those continuing to smoke CC, using one-sided test with 2.5% type I error probability.

The sample size is sufficient to obtain 95% CIs for the ratio between (geometrical) mean levels of primary BoExp in THS 2.2 and SA with upper and lower limits deviating not more than 18% from the point estimates, with an 80% overall probability of achieving the desired precision of estimating the true mean.

This study has 80% power using a one-sided test with 2.5% type I error probability:

1. To detect a 0.631 [mL/min/kg] (29%) difference between THS 2.2 and CC in CYP1A2 activity, as measured by the CAF clearance, assuming a standard deviation (SD) of 0.564. Effect size and variability are derived from data obtained in the YVD-CS01-EU study sponsored by PMI.
2. To detect a 24.71 [ng/g creatinine] (20%) difference between THS 2.2 and CC in 11-DTX-B2, assuming a SD of 43.78. The anticipated effect size of THS 2.2 is assumed to be about 90% of the effect of smoking cessation.

9 CHANGES FROM THE PROTOCOL SPECIFIED STATISTICAL ANALYSIS

- Shift tables for safety endpoints will not be produced for this study, the relevant information will be provided in listings.
- Statistical analysis for blood COHb (%) and exhaled CO (ppm) measurements and the QSU-brief questionnaire data, MNWS questionnaire data and the MCEQ questionnaire data will be performed including interaction terms for product and time point to enable least square means to be calculated at each time point in order to explore the pattern of the THS 2.2 effect over time. The main comparison between products will be the comparison over all time points.
- The second exploratory objective (“To evaluate in smokers switching from CC to THS 2.2, smokers continuing smoking CC and smokers switching from CC to SA the relationship between:

- Primary and secondary BoExp and NEQ
- Selected risk markers and, primary and secondary BoExp, and NEQ

will now only investigate:

- 1) The relationship between primary and secondary BoExp and NEQ, which will be reported in a separate report.
- 2) The relationship between risk markers and NEQ, which will be reported in the CSR.

- The term “adjusted to creatinine” has been replaced by “adjusted for creatinine” in all relevant endpoints and analyses.

10 ANALYSIS POPULATIONS

The main population for non-safety analysis will be the full analysis set (FAS). The Per-Protocol (PP) Population will be used only for the analysis of the primary endpoint to examine the robustness of the primary analysis. As there is not expected to be major differences between the FAS and PP Population for this study the PP Population will only be assessed if there are more than 10 subjects excluded from the PP Population.

Safety data will be analyzed using the Safety Population.

10.1 Full Analysis Set

The FAS consists of all the randomized subjects who had at least one post-randomization product use experience, if randomized to THS 2.2 or CC, and have at least one valid BoExp measurement (THS 2.2, CC, SA arms).

